Implicit review forms: Guided by the RAND DRG project's implicit review form, we will develop a structured implicit review form that elicits judgments from reviewers for defined items for each non-tracer condition episode of care. An example of an item is "rate the quality of care for this episode of care on a 5-point scale." Baseline encounter data will be available at the start of the project for use in developing this form. This form will also request information about the factors that influenced the quality rating, and this will be coded for all implicit review forms.

REFERENCES

- 7) U.S. Government Accountability Office (GAO). *VA Health Care: VA has taken steps to make services available to women Veterans, but needs to revise key policies and improve oversight processes.* GAO-10-287, Washington, DC, March 2010. Available at www.gao.gov.
- **8) Washington DL**, **Bean-Mayberry B**, Mitchell MN, Riopelle D, **Yano EM**. Tailoring VA Primary Care to Women Veterans: Association with patient-rated quality and satisfaction. *Women's Health Issues*. 2011;21(4S):S112-9.

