Pension Record Interchange (CAPRI), which provides direct access to VistA medical records (Computerized Patient Record System, CPRS) from multiple VistA systems with a single access/verify code⁵¹⁻⁵³ Through the VINCI system, we will obtain from CDW lists of all patients seen within participating site healthcare systems within our data collection periods. We will maintain these lists in VINCI workspace. From these lists, we will identify patients seen by DWHPs so that we can describe characteristics of their patient populations. We will then identify the subset of DWHP female patients with the study tracer conditions for quality assessment. To do this, we will use ICD9 codes, CPT codes, and, for some conditions, consult requests, medications prescribed, and/or laboratory tests ordered, in combination with the previously described DWHP list. For these patients, we will collect patient demographics, provider(s) associated with each encounter, clinic stop codes (which identifies the clinic type), and all EMR notes, orders, consult requests, and test results (e.g., laboratory, pathology, radiology) for our data collection periods. This data will be downloaded to the VA GLA Research Server.

EMR de-identification for blinded review: Nurse abstractors and implicit reviewers will be blinded to whether the episodes of care that they are reviewing are from the intervention or control periods. During an initial training period, all records will be reviewed by supervising research staff. After this initial training period, for the duration of the data collection period, records will be randomly spot-checked to verify adherence to the protocol.

Quality of Care – Guideline-adherent care classification procedure: We will conduct medical record abstraction to identify a sample of episodes of care for tracer clinical conditions. We will categorize care as guideline-adherent versus not guideline-adherent. The tracer conditions will be evaluation/management of: abnormal uterine bleeding;⁵⁵⁻⁵⁸ menopause management, and urinary incontinence.⁶⁹ To determine if the care is or is not guideline-adherent, we will develop quality measurement tools. The methods we will use to develop these tools are described below in Specific Aim #4.

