Trained chart abstractors will review each chart to complete the chart abstraction templates with the information requested. They will not be making a direct determination of care quality or efficiency, but rather obtaining the information for a computerized algorithm that will do this. A WH specialist will be available to them to answer questions that may arise. We will develop a database (using REDcap software) so that data may be entered directly into REDcap via a study computer. Senior research staff who are clinicians will randomly spot-check chart abstraction data, throughout the data collection period, to verify adherence to study protocols.

Independent Variables: *DWHP characteristics* may influence the quality and efficiency of the care that they provide, as well as their response to the intervention. We will extract DWHP characteristics from the Personnel and Accounting Integrated Data System (PAID) Master File, which contains the human resources data for all VA employees, including provider gender, age, education and licensure (MD, NP, PA), and medical specialty. We will obtain *characteristics of patients* seen by the DWHP in the study period from VA administrative data. This data will include: female caseload (# of uniques) and workload (# of encounters), female percent of total caseload and workload. We will derive percent of female workload by age category (<45, 45-64, 65+, corresponding to reproductive age group, age for emergence of chronic conditions, and older).

Aim #1 Statistical Analysis: We will calculate descriptive statistics of the proportion of CBOC women's primary care that is guideline-adherent. We will examine each of these descriptive statistics by clinical condition, and conduct z-tests for differences in proportions between conditions. We will also evaluate a series of logistic regressions to test for association of the composite measure of quality with each of the various independent variables in order to build a predictive model. Because of the hierarchical nature of the data (episode of care within patient within DWHP), a generalized linear model (GLM) approach using a logit link will be used to estimate and test the significance of the regression coefficients.

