For the analysis of the intervention effect over time, we will conduct a modified stepped-wedge analysis. This analysis takes into account the hierarchical nature of the data, with episodes of care occurring over time, and being nested within DWHPs. In the stepped wedge analysis, calendar time is divided into steps, corresponding to the time periods when providers are initially exposed to the intervention.

Sample Size and Power Calculations: The power calculations are predicated on the goal of evaluating the performance of DWHPs through the episodes of care they see. There are two levels of clustering: DWHPs within healthcare systems and episodes of care within DWHPs. We are making the assumption that there is little or no correlation between the DWHPs. As a result, we performed the calculations via the single level of clustering within DWHPs, with the episode of care as the unit of analysis. We will assume two values for the intra-cluster correlation coefficient (ICC): 0.03 and 0.05. The latter is relatively large compared to results that have been reported in the literature. The calculations assume a two-tailed 5% significance level and power of 80% to detect a difference between the study arms (with the study arm referring to intervention versus control, and including all data collection in each of those study periods, respectively). The statistical test involved is a simple z-test for the comparison of two proportions, but the actual analysis will be more sophisticated using covariates and adjusting for the actual number of episodes seen by a given DWHP. Thus, it can be assumed that the sample size calculations presented here are conservative.

With a baseline estimate from our preliminary data that 67% of episodes of care are fully proficient, then with 25 episodes of care per DWHP, we could detect small to medium effects of the intervention (see Table 2). If the baseline proficiency was 80%, then we could detect a medium size intervention effect, whereas if the baseline proficiency was 50%, we could detect a very small effect. If we increased the number of eligible episodes of care from which to measure proficiency to 50 per DWHP, then with a baseline proficiency of 67%, we could detect a small intervention effect. The number of available DWHPs (approximately 20 per study arm) and episodes of care provides us with >80% power.

Table 2: Number of DWHPs needed to detect the effects in each scenario with 80% power

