Aim #4: To develop tools to measure quality of WH care in VA.

To complete the work in Aim 1, we will need to develop tools to measure the quality of WH care in VA. VA monitors two gender-specific quality indicators as part of its annual External Peer Review Program performance monitoring – timely receipt of breast and cervical cancer screening. Though relatively easy to measure, there is little variation in these quality indicators across VA sites. ⁷⁶ Therefore, we have selected alternate gynecology tracer conditions for our quality assessment. Explicit evidence-based quality guidelines exist for each of the selected tracer conditions (abnormal uterine bleeding; ⁵⁵⁻⁵⁸ counseling in patients prescribed teratogenic medications, contraception counseling and management; ^{60,61} preconception counseling; ⁶⁶⁻⁶⁸ menopause management, and urinary incontinence. ⁶⁹). The goal of Aim 4 is to operationalize these guidelines into quality measurement tools. The process for achieving this aim consists of four steps – translating guidelines, defining CPRS data sources and elements, developing EMR abstraction forms, and creating computer programs based on specifications. ⁷⁷ Serial testing and revising will be done within each step.

Translating Guidelines: We will first construct, modify, or augment the algorithm for each guideline. Next, we will translate each guideline into a series of binary "if/then" statements. The will also define terms as needed for clarifying these if/then statements. Two investigators will independently draft these "if/then" statements for each guideline and then reconcile their statements, discussing differences, to form for each guideline one draft series of if/then statements. To validate these if/then statements, these drafts and the guidelines and algorithms associated with them will then be given to members of our quality measurement tool validation, who will comment on our interpretation of the guidelines (to create the algorithm and specify terms) and our if/then statements, and then back-translate them to reconstruct quality guidelines. There are discrepancies between the versions reconstructed by our panel members, and the actual guidelines, we will investigate the source of these discrepancies and modify/clarify our if/then statements as needed. We will do this serially until we have a final set of validated if/then statements and associated definitions.

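### Z-tests between tracer conditions ignore the clustering the plan describes, so their standard errors and p-values do not match the data; direction and size depend on inputs not given

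*Combined protocol and SAP*

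**What the plan says.** The Aim #1 Statistical Analysis section describes guideline adherence by clinical condition and will "conduct z-tests for differences in proportions between conditions". It gives no clustering adjustment, multiplicity rule or significance level for these tests. The same paragraph goes on: "Because of the hierarchical nature of the data (episode of care within patient within DWHP), a generalized linear model (GLM) approach" with a logit link is to be used, but only for the regression coefficients of the predictive model.

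The Quality of Care classification procedure under Aim 1 names three tracer conditions: "abnormal uterine bleeding;⁵⁵⁻⁵⁸ menopause management, and urinary incontinence". Aim #4 has a longer list of six, adding preconception counseling and "counseling in patients prescribed teratogenic medications, contraception counseling and management".

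The only stated significance level is in Sample Size and Power Calculations, for the comparison of study periods: "The calculations assume a two-tailed 5% significance level and power of 80% to detect a difference between the study arms". That section also gives the clustering inputs: "We will assume two values for the intra-cluster correlation coefficient (ICC): 0.03 and 0.05".

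**The concern.** The plan recognises dependence among episodes for one analysis and leaves it out of another that uses the same episodes. A two-proportion z-test takes its variance from the number of episodes alone. Here the same DWHPs may supply episodes of several conditions, and a patient may supply more than one episode. The variance of a difference between conditions therefore depends on how DWHP skill and caseload vary by condition.

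At stake is whether a reported difference in adherence between, say, menopause management and urinary incontinence can be told from chance, and whether its confidence interval has the right width. A second, smaller matter is that several pairs are tested with no rule for reading them together.

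**Working it through.** **Inputs from the documents.** Three conditions, hence 3 pairs (Aim 1); baseline proficiency 67%, ICC 0.03 or 0.05, about 20 DWHPs per study arm, and 25 or 50 episodes per DWHP per arm (sample size section and Table 2).

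**Assumptions.** Each healthcare system contributes to both periods, so I take the same 20 DWHPs with 50 or 100 episodes each in total. Each test is two-sided at 5%. I apply the plan's ICC within a condition. Condition mix and the condition-specific share of DWHP skill are not given and are varied. Within-patient correlation is not given and is left out.

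**1. The plan's own figure.** For 67% v 77%, n per arm = [1.96√(2·0.72·0.28) + 0.8416√(0.67·0.33 + 0.77·0.23)]² / 0.10² = (1.2446 + 0.5311)² / 0.01 ≈ 315.3, rounded up to 316. With 25 episodes and ICC 0.03 the design effect is 1 + 24·0.03 = 1.72, and 316·1.72/25 = 21.7; Table 2 says 22. All 16 cells agree within one DWHP. So the plan does correct for clustering when it sizes the arm comparison.

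**2. Multiplicity alone.** Three independent tests give 1 − 0.95³ = 14.3%. The three pairs share data, and simulation with no clustering gives 11–12%.

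**3. Clustering, even condition mix.** Let m be the episodes per DWHP, n = m/3 the episodes of one condition per DWHP, ρ the ICC within a condition, and ρ_b the correlation between episodes of different conditions in the same DWHP. Relative to the z-test's variance, the true variance of the difference is

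D = 1 + (n − 1)ρ − nρ_b, and the true per-pair error is 2Φ(−1.96/√D).

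Example: m = 50, ρ = 0.05, ρ_b = 0. Then D = 1 + 15.67·0.05 = 1.78, 1.96/√1.78 = 1.47, and the error is 14.2%. Simulation (10,000 runs) also gives 14.2%.

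| Condition-specific share of DWHP variance | m=50, ICC 0.03 | m=50, ICC 0.05 | m=100, ICC 0.03 | m=100, ICC 0.05 |
|---|---|---|---|---|
| none (ρ_b = ρ) | D 0.97, 4.7% | D 0.95, 4.4% | D 0.97, 4.7% | D 0.95, 4.4% |
| one quarter (ρ_b = 0.75ρ) | D 1.10, 6.1% | D 1.16, 6.9% | D 1.22, 7.6% | D 1.37, 9.4% |
| half (ρ_b = 0.5ρ) | D 1.22, 7.6% | D 1.37, 9.4% | D 1.47, 10.6% | D 1.78, 14.2% |
| all (ρ_b = 0) | D 1.47, 10.6% | D 1.78, 14.2% | D 1.97, 16.3% | D 2.62, 22.6% |

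In the first row the shared DWHP effect cancels from the difference, which is why the test is slightly conservative there.

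**4. Uneven condition mix (simulated, 20 DWHPs, 50 episodes, mixes drawn at random).** At ICC 0.03 and 0.05, per-pair error is 9.5% and 12.0% with fully shared skill, and 11.4% and 15.3% with half-shared skill. The chance of at least one false difference among three pairs is 21.4% and 26.6%, and 25.3% and 32.6%. Fully condition-specific skill with uneven mixes at 100 episodes and ICC 0.05 brings per-pair error to about 27%, depending on how uneven the mix is. Over these settings the range is roughly 6–27% per pair and 14–51% for at least one false difference.

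**5. Is a multiplicity correction enough?** Bonferroni (0.05/3 = 0.0167 per test) gives about 4% family-wise without clustering. With 20 DWHPs and 50 episodes it leaves 7.5–10.1% (half-shared, even mix), 11.9–17.2% (condition-specific, even mix) and 10.1–13.4% (shared, uneven mix). The variance has to be corrected as well.

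**The case against.** The strongest reply is that conditions are compared largely within the same DWHPs, so a shared DWHP effect cancels. This stands. A reader might infer from the word clustering that differences will be declared too often. The documents do not support that, because they give neither the condition mix nor the degree of condition-specific skill that inflation requires. They do give some reason to doubt the benign case. The plan collects the age split of each DWHP's female workload, menopause care is age-linked, and the self-assessment tool rates 15 clinical content areas separately. None of this supplies a number, so the 6–27% remains a set of scenarios.

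A reader might also take the 5% level as planned for these tests; it is stated only for the arm comparison. Likewise, the Aim #4 list would give 6·5/2 = 15 pairs, and 1 − 0.95¹⁵ = 53.7% if they were independent. But Aim 1 names three conditions, and pairs that share data would give less. The two lists should be reconciled in any case.

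It can be said that the sample size section already promises a fuller analysis than a simple z-test. That remark concerns the arm comparison, so it does not cover this one.

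Finally, adherence is all-or-none over each condition's own set of statements, so exactly equal proportions are an unlikely null and these comparisons are close to descriptive. This limits the practical weight of the type I error. It does not help the confidence intervals: with an even mix and half to fully condition-specific skill, the true standard error is √1.22 to √2.62, or 1.10 to 1.62, times the one used.

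**Conclusion.** The point holds as a mismatch between a stated method and the structure of the data that the plan itself describes. It is more than missing detail, because the plan names a test whose independence assumption its own paragraph contradicts. The effect of clustering runs from slight conservatism to substantial inflation, and the documents do not show where in that range the trial will fall. Only the multiplicity figure needs no clustering assumption, and it rests on the assumed 5% level and three pairs.

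The consequence is secondary. A reader might infer that the test of DWHP Support is undermined. It is not: the stepped-wedge analysis is separate and is said to account for nesting within DWHPs.

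**What to change.** In the Aim #1 Statistical Analysis section, replace the z-tests with a tracer-condition factor in the planned logit model. State how DWHP and patient clustering enter, since a generalized linear model with a logit link does not by itself account for it. Use random effects, or GEE with a small-sample correction because there are only about 20 DWHPs. Allowing the DWHP effect to differ by condition would cover condition-specific skill.

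Test condition once jointly (2 degrees of freedom for three conditions), and examine pairwise contrasts only if that test is significant. With three conditions this controls the family-wise error, so a further correction is optional; use Holm if more conditions are compared. State the significance level and which condition list applies. Keep the raw proportions by condition as description.

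The cost is a change of SAP wording and a little more analysis work, with no new data. Some p-values may become less favourable.

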This proposed research project was developed in partnership with VA Patient Care Services' Women's Health Services (WHS) and Specialty Care Services (SCS), VISN 22, and VA Greater Los Angeles Healthcare System. It will impact VA practice and policies in women Veterans' health care, access, and quality (HSR&D priority areas) as well as other specialty areas. Further, it will advance science in both WH care quality measurement and the delivery of health care through non-face-to-face interactions.

Research Design and Methods

Study Design and Overview: We propose to conduct a prospective, modified stepped wedge trial of *DWHP Support* for DWHPs in healthcare systems that participate in Gynecology SCAN-ECHO and have gynecology e-consults. To accommodate facility and VISN needs, we will work with our facility and women's health partners to stage the assignments for the stepped wedge rollout (i.e., it will not be randomized). We will introduce the intervention throughout one healthcare system at each step, with the intervention being directed to all DWHPs in that healthcare system.

We will use a mixed methods analytic approach to measure the intervention's effect, while also evaluating the

implementation processes and use of the intervention. Therefore, while testing *DWHP Support* effectiveness, this study will also advance our understanding of the context for its implementation, which can support its broad implementation in VA, as well as inform future trials. An advantage of our modified stepped wedge approach is that our intervention will occur in the "real world", i.e., not in a highly controlled experimental setting; this enhances the potential external validity of the intervention and thereby increases the possibility that the intervention could feasibly be spread to other VISNs, should it prove effective.

Setting and Participants: *DWHP Support* will be implemented in healthcare systems in VISN 22 and at other VA sites nationally. VISN 22 encompasses Southern California and the Las Vegas area. It has a racially and ethnically diverse women Veteran population, with 68% non-Hispanic White, 5% non-Hispanic Black, 21% Hispanic, and 6% other racial/ethnic groups.⁴⁵ The participants will be DWHPs in those settings.

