Overview of Data Sources, Data Collection Time Points, and Key Measures: The data sources, data collection time points, and key measures to achieve our specific aims are discussed by specific aim, and

summarized in Table 1 below.

Table 1: Data sources, data collection time points, and key measures by research specific aim

Data sources	Data collection time point(s)	Key Measures				
Aim 1: Effect of DWHP Support on care quality and efficiency						
Electronic medical records	Baseline & throughout implementation*	Quality of Care: Proportion of care that is guideline-adherent; Efficiency of Care: Proportion of in-person specialist visits that are preventable				
Aim 2: Impact in changing provider behavior, self-rated WH knowledge, skills, and self-efficacy						
E-consult referring provider brief survey	After each e- consult	Change in patient management for patient who is the subject of the SCAN/e-consult; change in provider knowledge				
DWHP self-assessment tool	Baseline and during implementation	DWHP self-rated WH knowledge, skills, and self-efficacy				
Aim 3: Attitudes about DWHP Support, its use, specialist time for implementation, other features						
Semi-structured interviews with DWHPs	Baseline and during implementation	Familiarity with SCAN-ECHO programs. Attitudes and beliefs regarding intervention; motivation and opportunity for its use. Familiarity with DWHP Support (reach and adoption) and other SCAN-ECHO programs; Influence of acceptability, usability, barriers and facilitators on use; Motivation and opportunity for sustained use				
Aim 4: Develop tools to measure quality of WH care in VA						
Clinical practice guidelines	To commence at start of study	Not applicable [chart abstraction templates will be produced]				

^{*}Electronic records from the baseline time periods will be assessed retrospectively

Specific Aim #1: To evaluate the effect of DWHP Support on WH care quality and efficiency using a stepped wedge design with sites participating in DWHP Support.

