We hypothesize that *DWHP Support* will improve the quality and efficiency of WH care in CBOCs. We expect that these effects may be influenced by baseline characteristics of the DWHPs (e.g., time in practice), patient conditions and characteristics, and practice characteristics, as well as DWHPs' use of the intervention. For this aim, our analytic sample will be limited to sites participating in DWHP Support outside of GLA, given that DWHP support was piloted in GLA and therefore does not have a recent "control" period (i.e., GLA was contaminated by the pilot). We will, however, use GLA data to pilot our electronic medical record (EMR) data abstraction procedures. We will also collect GLA e-consult data because this data were not contaminated by the piloting of SCAN-ECHO at GLA.

Dependent Variables: The main outcome measures will be quality of care defined by adherence to practice guidelines. We will assess quality of care and efficiency of care using the VA electronic medical records (EMR) of all female patients seen by DWHPs during the data collection period. With the modified stepped wedge design, each participating site healthcare system is contributing data to both intervention and control periods, thereby addressing comparability concerns. We expect to identify multiple episodes of care per DWHP over the combined data collection periods, where we define an episode of care as the care initiated by the DWHP for a WH condition, irrespective of whether it occurs over one or multiple encounters, and is face-to-face or not.⁵⁴

Electronic medical record (EMR) data abstraction: To assemble the relevant data from the EMR using the VHA Health Information Access (HIA) program's Data Use Agreement protocols, we will use the *Corporate Data Warehouse (CDW)*, accessed through VINCI and discussed above and, as needed, the Compensation and

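### The Aim 1 adherence proportions and predictor regressions are not tied to a study period, so followed as written they mix control and intervention episodes and leave out exposure

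*Combined protocol and SAP*

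**What the plan says.** The Aim 1 sample spans both periods. Table 1 gives the record collection time points as "Baseline & throughout implementation". Under Dependent Variables, "each participating site healthcare system is contributing data to both intervention and control periods", and the investigators expect "multiple episodes of care per DWHP over the combined data collection periods".

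The Aim #1 Statistical Analysis then has two parts.

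- **Descriptive and predictor analyses.** The plan calculates "descriptive statistics of the proportion of CBOC women's primary care that is guideline-adherent" and adds: "We will examine each of these descriptive statistics by clinical condition". Conditions are compared by z-tests. Logistic regressions follow, to "test for association of the composite measure of quality with each of the various independent variables in order to build a predictive model". The paragraph headed Independent Variables lists provider gender, age, education and licensure, specialty, female caseload and workload, and the age mix of that workload. Study period, step, calendar time and exposure are not listed. The hierarchy named for these models is episode, patient and DWHP.
- **Intervention effect.** "For the analysis of the intervention effect over time, we will conduct a modified stepped-wedge analysis". Calendar steps and first exposure appear only here.

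On rollout, Study Design and Overview says the order is staged with partners and not randomized: "We will introduce the intervention throughout one healthcare system at each step".

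**The concern.** Two consequences follow if the first part is carried out as written.

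First, the plan hypothesizes that DWHP Support raises adherence. If it does, a proportion taken over both periods is a weighted average of usual-care and supported-care adherence. The weight is the share of intervention episodes that happened to be sampled. The figure would be reported as the quality of CBOC women's care but would estimate neither state. The z-tests between conditions share the problem if the period mix differs by condition.

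Second, the predictor models omit the one factor the trial expects to change the outcome. Whole systems cross over at different steps in a non-random order. If a trait such as licensure or specialty is more common in systems with a larger intervention share, it can appear as a predictor because of rollout timing alone. The plan also says DWHP characteristics may affect the response to the intervention. A model without exposure cannot separate that from an association with quality in general.

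**Working it through.** **The plan's own figure.** Table 2 supplies the scenario used below, so it was checked first. For 67% versus 77% (two-sided 5%, 80% power, pooled-variance z-test), n = 316 episodes per arm. Multiplying by 1 + (m − 1) × ICC and dividing by m gives:

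- m = 25: 316 × 1.72 / 25 = 21.7 and 316 × 2.20 / 25 = 27.8
- m = 50: 316 × 2.47 / 50 = 15.6 and 316 × 3.45 / 50 = 21.8

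Rounded up, these are 22, 28, 16 and 22, as stated. Table 2 is not in dispute here.

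**Inputs.** From the documents: control 67%, intervention 77% (or 83%), ICC 0.03 and 0.05, about 20 DWHPs per arm, and 50 episodes per DWHP (the larger Table 2 count). The plan's fully proficient percentage stands in for the adherence proportion. Assumed, because the documents do not give them: the period shares, the distribution of traits across systems, 20 DWHPs in total, and a 10/10 split on the trait.

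**Pooled proportion.** With intervention share w, p = 0.67 + 0.10w:

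- w = 0.20: 69%
- w = 0.50: 72%
- w = 0.80: 75%

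For 67% to 83%, p = 0.67 + 0.16w, which gives 70.2%, 75% and 79.8%.

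**Trait with no true effect.** Take two equal groups of systems. In one, a fraction s of episodes is intervention and a fraction q of DWHPs has the trait; in the other the fractions are 1 − s and 1 − q. Then:

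- share for DWHPs with the trait = qs + (1 − q)(1 − s)
- share for DWHPs without it = (1 − q)s + q(1 − s)
- spurious difference = effect × (2q − 1)(2s − 1)

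The bias is therefore a product of two imbalances. At q = s = 0.80 the shares are 0.68 and 0.32, and the difference is 0.10 × 0.6 × 0.6 = 0.036.

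**False-positive rate.** With correct DWHP-level errors, SE = √[2 × p(1 − p) × (ICC + (1 − ICC)/50) / 10]. At p = 0.72 this is 0.0446 (ICC 0.03) or 0.0527 (ICC 0.05). With t = difference / SE, the rate is Φ(t − 1.96) + Φ(−t − 1.96).

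| Imbalance (trait and share) | Difference, 67% to 77% | OR | False-positive rate |
|---|---|---|---|
| equal | 0 points | 1.00 | 5% |
| 60/40 on both | 0.4 points | 1.02 | about 5.1% |
| 70/30 on both | 1.6 points | 1.08 | 6.1 to 6.5% |
| 80/20 on both | 3.6 points | 1.20 | 10.5 to 12.7% |

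Under 67% to 83% (SE at p = 0.75: 0.0430 or 0.0509), 60/40 gives 0.6 points and 5.2 to 5.3%. 70/30 gives 2.6 points and 8.0 to 9.1%. 80/20 gives 5.8 points, OR 1.36 and 20 to 27%.

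**The case against.** The plan does not say that it pools the periods. It names no period for these analyses, so a baseline-only intent is possible. The list of independent variables is not called exhaustive. The text mentions response to the intervention, which would need exposure in some model, and the sample-size section promises covariates in the actual analysis. The regressions could be a step towards choosing those covariates.

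Part of this stands: pooling is inferred from the lack of any restriction, stratifier or period term. The replies do not supply what is missing. A baseline-only intent is nowhere written. The promised covariates are unnamed, and that sentence contrasts the sample-size z-test with the comparison of study arms. Choosing covariates through regressions that omit exposure leaves the same weakness in the choice.

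A reader might also infer that early systems supply mostly intervention episodes and late systems mostly control episodes. The documents do not support that. They give no number of steps, window lengths or period shares. Every system contributes to both periods, baseline records are assessed retrospectively, and only a sample of episodes is abstracted, so period shares could be balanced. Table 2 can even be read as equal episode counts per DWHP in each arm. With equal shares the period confounding of traits disappears, though the mixed proportion remains.

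**Conclusion.** The point holds as a minor one. As written, the adherence proportion lies somewhere between usual and supported care, at a place set by the episode mix: 69% to 75% for intervention shares of 20% to 80% under 67% to 77%. That needs only a real intervention effect and a sample from both periods.

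The trait confounding is conditional. It needs a trait and the intervention share both to differ between systems. Under 67% to 77%, moderate imbalance is almost harmless (about 5.1% false positives at 60/40, 6 to 6.5% at 70/30). The 10 to 13% figure needs 80/20 on both. These shares are assumptions, not features of the plan.

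It would be wrong to infer that the trial's estimate of the intervention effect is compromised. That estimate has its own stepped-wedge analysis organized by calendar step, which this point does not touch. What is affected is the descriptive reporting and the predictor models.

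**What to change.** In the Aim #1 Statistical Analysis:

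- Report the guideline-adherent proportion, overall and by condition, separately for control and intervention periods.
- Include intervention status and calendar step in every predictor regression. If predictors of usual-care quality are what is wanted, say so and fit those models to control-period episodes only.

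The cost is SAP wording and a little more analysis, with no new data. The added terms use a few degrees of freedom. A control-only fit avoids them but uses fewer episodes.
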